7.6. Second Malignancy

A second malignancy is one unrelated to the treatment of a prior malignancy (and is **NOT** a metastasis from the initial malignancy). Second malignancies require **ONLY** routine AE reporting unless otherwise specified.

7.7. Pregnancy, Contraception, and Risk of Embryo-Fetal Toxicity

Lenalidomide, a thalidomide analogue, caused limb abnormalities in a developmental monkey study. Thalidomide is a known human teratogen that causes severe life-threatening human birth defects. If lenalidomide is used during pregnancy, it may cause birth defects or embryo-fetal death. Carfilzomib can cause fetal harm based on findings from animal studies and the drug's mechanism of action. There are no adequate and well-controlled studies in pregnant women using carfilzomib. It is not known what effects KRT-232 (AMG 232) has on human pregnancy or development of the embryo or fetus. Therefore, female patients participating in this study should avoid becoming pregnant, and male patients should avoid impregnating a female partner.

Nonsterilized female patients of reproductive potential must agree to one of the following through defined periods during and after study treatment as specified below. Non-reproductive potential is defined as female subjects who are permanently sterile or are post-menopausal (no menses in 12 consecutive months without an alternative medical cause).

- Agree to practice 2 effective methods of contraception from the time of signing of the informed consent form through 5 weeks after the last dose of study drug. This includes one highly effective form of contraception and one additional effective contraceptive method (see examples below).

Highly effective methods:

- Intra-uterine devices (IUD)
- Hormonal (birth control pills/oral contraceptives, injectable contraceptives, contraceptive patches, or contraceptive implants)

Other effective methods (barrier methods):

- Latex or non latex condom with or without a spermicidal agent
- Diaphragm with spermicide; Cervical cap with a spermicide; Sponge with a spermicide OR

- Agree to practice true abstinence, when this is in line with the preferred and usual lifestyle of the subject. (Periodic abstinence [eg, calendar, ovulation, symptothermal, postovulation methods] and withdrawal are not acceptable methods of contraception.)

Male patients, even if surgically sterilized (ie, status postvasectomy) must agree to one of the following defined periods during and after study treatment as specified below.

- Agree to practice effective barrier contraception during the entire study treatment period and through 90 days after the last dose of study drug, OR
- Agree to practice true abstinence, when this is in line with the preferred and usual lifestyle of the subject. (Periodic abstinence [eg, calendar, ovulation, symptothermal, postovulation methods for the female partner] and withdrawal are not acceptable methods of contraception.)

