--	--

	
therapy, and previously treated/eradicated hepatitis C virus are eligible for study.
 
16. Subjects positive for human immunodeficiency virus (HIV) are NOT excluded from this study, but HIV-positive subjects must have:
 
A stable regimen of highly active anti-retroviral therapy (HAART)No requirement for concurrent antibiotics or antifungal agents for the prevention of opportunistic infections.A CD4 count above 250 cells/mcL and an undetectable HIV viral load on standard PCR-based test 
17. Men and women of reproductive potential who are unwilling to practice acceptable methods of effective birth control while on study through 5 weeks (women) or 3 months (men) after receiving the last dose of KRT-232 (AMG 232). Acceptable methods of effective birth control include sexual abstinence (men, women); vasectomy; or a condom with spermicide (men) in combination with barrier methods, hormonal birth control or IUD (women).
 
18. Pregnant women are excluded from this study because KRT-232 (AMG 232) is an agent with the potential for teratogenic or abortifacient effects. Because there is an unknown but potential risk for adverse events in nursing infants secondary to treatment of the mother with KRT-232 (AMG 232), breastfeeding should be discontinued if the mother is treated with KRT-232 (AMG 232). These potential risks may also apply to other agents used in this study.
 
19. Women who are lactating/breast feeding or who plan to breastfeed while on study through 1 week after receiving the last dose of study drug.
 
20. Subjects with prior treatment with an MDM2 inhibitor.

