3.1.14. The effects of KRT-232 (AMG 232) on the developing human fetus are unknown. For this reason and because lenalidomide is known to be teratogenic, women of child-bearing potential must commit to either abstaining continuously from heterosexual sexual intercourse or agree to use 2 forms of adequate contraception or continuously abstain from the time of informed consent for the duration of study participation through 5 weeks (women) after receiving the last dose of KRT-232 (AMG 232), lenalidomide, or carfilzomib. Should a woman become pregnant or suspect she is pregnant while she or her partner is participating in this study, she should inform her treating physician immediately. Men treated or enrolled on this protocol must also agree to use adequate contraception prior to the study, for the duration of study participation, and 3 months after completion of KRT-232 (AMG 232) administration. This includes one highly effective form of contraception (e.g. intrauterine device [IUD], hormonal [birth control pills, injections, hormonal patches, vaginal rings or implants] or partner's vasectomy) and one additional effective contraceptive method (e.g. male latex or synthetic condom, diaphragm, or cervical cap).

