In pooled human liver microsomes, AMG 232 (KRT 232) and M1 are moderate inhibitors of UGT1A1. In human hepatocytes, UGT1A1/3/4 enzymatic activities were increased by AMG 232(KRT 232) at concentration $> 5 \mu\text{m}$ and the mRNA transcripts were minimally increased by AMG 232 (KRT 232) at concentration $\geq 10 \mu\text{m}$. Since the exposure of AMG 232 is expected to be low (unbound $C_{\max} = 0.161 \mu\text{m}$ at 480 mg), an increase in metabolism and CL via auto-induction are not expected.

AMG 232 (KRT 232) is not a BCRP substrate. Although AMG 232 (KRT 232) is an inhibitor of OAT3 (moderate to potent), OATP1B1 (moderate to potent), OATP1B3 (moderate to potent), OAT1 (moderate), BCRP (very weak), OCT2 (very weak), and P-glycoprotein (moderate), the ratios of unbound C_{\max} to the in vitro IC_{50} is low (<0.03) at the proposed doses; thus, the potential for AMG 232 (KRT 232) to cause transporter-mediated DDIs due to inhibition of the transporter is low.

Patient Care Implications

Advise women study participants of reproductive potential to use effective contraception while receiving AMG 232 (KRT 232) and 1 month + 1 week (or 5 weeks) after the last dose of AMG 232 (KRT 232). Men study participants must continue to use contraception for 3 months and 1 week (or 13 weeks) after the last dose of AMG 232 (KRT 232). Refer to the protocol document for specific guidance.

Availability

KRT-232 (AMG 232) is an investigational agent supplied to investigators by the Division of Cancer Treatment and Diagnosis (DCTD), NCI.

KRT-232 (AMG 232) is provided to the NCI under a Collaborative Agreement between the Pharmaceutical Collaborator and the DCTD, NCI (see Section 12.3).

Agent Ordering and Agent Accountability

NCI-supplied agents may be requested by the responsible investigator (or their authorized designee) at each participating institution. Pharmaceutical Management Branch (PMB) policy requires that agent be shipped directly to the institution where the subject is to be treated. PMB does not permit the transfer of agents between institutions (unless prior approval from PMB is obtained). The CTEP-assigned protocol number must be used for ordering all CTEP-supplied investigational agents. The responsible investigator at each participating institution must be registered with CTEP, DCTD through an annual submission of FDA Form 1572 (Statement of

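### The rules on male contraception conflict: vasectomy is accepted in the synopsis but gives no exemption in 7.7, and the post-treatment period in 7.7 runs from an undefined study drug

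*Combined protocol and SAP*

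**What the plan says.** Four places in the combined protocol and SAP set contraception rules for men.

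- **Synopsis, exclusion 17** excludes those unwilling to use birth control on study and "through 5 weeks (women) or 3 months (men) after receiving the last dose of KRT-232 (AMG 232"). It continues: "Acceptable methods of effective birth control include sexual abstinence (men, women); vasectomy", with a condom plus spermicide as a further option for men.
- **Section 3.1.14** (same text in synopsis inclusion 14) requires men to use contraception "for the duration of study participation, and 3 months after completion of KRT-232 (AMG 232) administration". The sentence that follows describes one highly effective form plus one additional method. The only vasectomy it mentions is a partner's.
- **Section 7.7** states: "Male patients, even if surgically sterilized (ie, status postvasectomy) must agree to one of the following". The options are an effective barrier method during treatment and "through 90 days after the last dose of study drug", or true abstinence.
- **Section 8.1**, under Patient Care Implications, asks men to continue "for 3 months and 1 week (or 13 weeks) after the last dose of AMG 232 (KRT 232"), and then refers the reader back to the protocol for specific guidance.

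Section 3.1.14 says that lenalidomide is known to be teratogenic. Section 7.7 says that it may cause birth defects or embryo-fetal death.

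**The concern.** These are eligibility and counselling rules in a regimen that contains a drug the protocol itself calls teratogenic. If the sections disagree, the same man can satisfy one and fail another. Sites working from different sections would then counsel men differently, and a monitor could not say which rule had been breached. Two disagreements matter: whether a vasectomy is enough, and which drug's last dose starts the post-treatment period. The length of the period looks like a third, but it turns out to be minor.

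**Working it through.** The protocol gives no figure to reproduce here. The check sets the passages side by side and then converts the periods to days.

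| Place | Vasectomised man | Counted from | Period |
|---|---|---|---|
| Synopsis exclusion 17 | vasectomy listed as acceptable | KRT-232 | 3 months |
| 3.1.14 and synopsis inclusion 14 | own vasectomy not mentioned; two methods described | KRT-232 | 3 months |
| 7.7 | not exempt; barrier or abstinence | *study drug* | 90 days |
| 8.1 | no method given | KRT-232 | 3 months and 1 week (or 13 weeks) |

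**Vasectomy.** Exclusion 17 separates vasectomy from the condom option by *or*, so it stands as an alternative. Section 7.7 removes that alternative. Exclusion 17 does not appear in the full list: 3.2.17 concerns HIV and 3.2.18 pregnancy. Section 3.1.14 matches neither text. It describes two methods where 7.7 accepts a barrier method alone, and it does not make a man's own vasectomy sufficient.

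**Anchor.** Section 7.7 does not define *study drug*. The evaluability rule in 5.6 ties the term to KRT-232 by giving its threshold as a count of KRT-232 daily doses. The medication diary (Appendix E) also applies it to lenalidomide and dexamethasone. Section 3.1.14 does not settle the matter: its period for women names KRT-232, lenalidomide or carfilzomib, while its period for men names KRT-232 only. Section 7.7 uses *study drug* for both sexes. Read as KRT-232 alone, the term agrees with 3.1.14 for men but not for women. Read as all three agents, it agrees for women but not for men.

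**Durations in days.**
- Three calendar months: 89 to 92 days (all start dates in 2023–2024).
- 90 days: 90.
- 13 weeks: 13 × 7 = 91.
- Three calendar months and one week: 89 + 7 = 96 to 92 + 7 = 99.
- Three 4-week months and one week: 84 + 7 = 91, which equals 13 weeks.

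**End of the period**, counted from Day 1 of a full final cycle. The study calendar and treatment plan give the last KRT-232 dose on Day 7, lenalidomide on Day 21 and dexamethasone on Day 22.
- 3 calendar months after KRT-232: 7 + 89 = Day 96 to 7 + 92 = Day 99.
- 13 weeks after KRT-232: 7 + 91 = Day 98.
- 3 calendar months and 1 week after KRT-232: 7 + 96 = Day 103 to 7 + 99 = Day 106.
- 7.7, if *study drug* is KRT-232 only: 7 + 90 = Day 97, within 2 days of Days 96–99 and 1 day from Day 98.
- 7.7, if it includes lenalidomide: 21 + 90 = Day 111, which is 12 to 15 days after Days 96–99.
- 7.7, if it also includes dexamethasone: 22 + 90 = Day 112, one day later still.

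If KRT-232 is stopped before the other agents, the gap between the anchors exceeds these 14 or 15 days.

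**The case against.** The strongest reply is that most of this is wording. A reader might infer three materially different durations, but 3 calendar months, 90 days and 13 weeks all lie between 89 and 92 days. A reader might also call 8.1 inconsistent in itself. Its preceding line for women equates one month plus one week with 5 weeks, so the paragraph works in 4-week months, and on that convention 13 weeks is correct. Section 8.1 also defers to the rest of the protocol. Both replies stand. What remains on duration is that the 4-week convention, if applied elsewhere, would turn 3 months into 84 days, 6 days short of 90, and that a calendar reading of 8.1 gives 96 to 99 days.

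A reader might infer a two-week spread as a fact. The documents do not support that without a condition: it needs *study drug* to include lenalidomide, and 5.6 points the other way.

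It can also be said that the periods do not exclude one another, since a man who follows the longest meets them all. Moreover, 3.1.14 covers the whole of study participation and 7.7 the whole treatment period, so lenalidomide exposure on study is covered under both. That is correct and limits the anchor question to the weeks after treatment. It does not tell a site which period is required.

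Finally, the text accepting vasectomy is a single synopsis item, and neither 3.1.14 nor 7.7 exempts vasectomised men. It would be too strong to say that opposite rules run throughout the protocol. The supplied text, however, does not say whether the synopsis or the body prevails, so the contradiction between exclusion 17 and 7.7 stands.

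**Conclusion.** The concern holds in two parts. First, exclusion 17 accepts vasectomy, 7.7 does not exempt vasectomised men, and 3.1.14 fits neither. No reading of dates or terms removes this. Second, the male period is anchored to KRT-232 in three places and to an undefined *study drug* in 7.7. The second part is worth about two weeks in a full final cycle if the term includes lenalidomide, and one to two days if it means KRT-232 only. These figures assume calendar months and that all drugs are given to their last scheduled day. The differences in duration wording are minor on their own.

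A reader might go further and infer a demonstrated risk to partners from a difference of days. No passage supports that. What is shown is that eligibility and compliance for men depend on which section is read. Sample size, dose-limiting toxicity rules, analysis sets and analyses are unaffected.

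**What to change.** Reconcile the synopsis, 3.1.14, 7.7 and 8.1 so that they state:

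- one rule for vasectomised men, with the same list of acceptable methods for men in each place;
- one anchor for the post-treatment period, with the drug or drugs named instead of *study drug*, and a deliberate decision on whether the anchors for men and women in 3.1.14 should differ;
- one duration, expressed in days.

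Either carry synopsis exclusion 17 into section 3.2 or remove it. Which method, anchor or period is right is for the sponsor and investigators to settle, and this review takes no position on it. The cost is amendment wording and matching changes to patient materials.

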8. PHARMACEUTICAL INFORMATION

A list of the adverse events and potential risks associated with the investigational or commercial agents administered in this study can be found in Section 7.1.

8.1. CTEP IND Agent(s)

Investigator Brochure Availability

The current versions of the IBs for the agents will be accessible to site investigators and research staff through the PMB Online Agent Order Processing (OAOP) application. Access to OAOP requires the establishment of a CTEP Identity and Access Management (IAM) account and the maintenance of an “active” account status and a “current” password. Questions about IB access may be directed to the PMB IB coordinator via email.

KRT-232 (AMG 232) (NSC 789723)

Chemical Name: 2-((3R,5R,6S)-5-(3-chlorophenyl)-6-(4-chlorophenyl)-1-((S)-1-(isopropylsulfonyl)-3-methylbutan-2-yl)-3-methyl-2-oxopiperidin-3-yl) acetic acid

International Non-Proprietary Name (INN): Navtemadlin

Classification: MDM2 inhibitor

Molecular Formula: C₂₈H₃₅Cl₂NO₅S **M.W.:** 568.55

Mode of Action: AMG 232 (KRT 232) is a small molecule, cytotoxic chemotherapeutic agent that binds to murine double minute chromosome 2 (MDM2) and inhibits the MDM2/tumor protein 53 protein-protein interaction.

Description: Is a slightly hygroscopic, anhydrous, and crystalline white to off-white powder.

How Supplied: Kartos Therapeutics supplies, and the Pharmaceutical Management Branch distributes AMG 232 (KRT 232) as an immediate release tablet formulated as either an uncoated tablet with a low drug load (LDL tablet) or a film-coated tablet with a high drug load (HDL tablet).

The current supply is uncoated tablet with a low drug load (LDL tablet):

- 15 mg tablet: white to off-white round
- 60 mg tablet: white to off-white oval

Future supply is film-coated tablet with a high drug load or HDL tablet. The HDL tablet drug label has a blue bar to differentiate from the LDL tablet bottle:

- 15 mg tablet: green round
- 30 mg tablet: light orange round
- 60 mg tablet: blue oval
- 120 mg tablet: purple oval

AMG 232 (KRT 232) supply is packaged as 30 tablets per high-density polyethylene bottle and closed with aluminum foil lined heat induction seals and polypropylene child-resistance closures. Inactive ingredients of the tablets are lactose monohydrate, microcrystalline cellulose, hydroxylpropyl cellulose, croscarmellose sodium, and magnesium stearate.

Preparation: AMG 232 (KRT 232) uncoated tablets (LDL tablet) can be dispensed in the original container or in pharmacy dispensing bottles. **The film-coated tablets (HDL tablet) must be dispensed in the original bottle.** There are no data to support the re-packaging of HDL tablets in containers other than the original bottle.

Storage: Store intact bottles according to the drug label.

Uncoated tablet (LDL tablet):

- AMG 232 (KRT 232) 15 mg Tablets: below 25°C (77°F), protect from light.
- AMG 232 (KRT-232) 60 mg Tablets: 15°C – 30°C (59°F - 86°F), protect from light

Film-coated tablet (HDL tablet): 15°C – 30°C (59°F - 86°F), protect from light.

If a storage temperature excursion is identified, promptly return AMG 232 (KRT 232) to the proper storage temperature and quarantine the supplies. Provide a detailed report of the excursion (including documentation of temperature monitoring and duration of the excursion) to [contact] for determination of suitability.

Stability: Shelf-life stability studies of AMG 232 (KRT 232) tablets are ongoing.

Route(s) of Administration: Oral.

Method of Administration: AMG 232 (KRT 232), uncoated (LDL) or coated (HDL) tablet, can be taken with a glass of water with or without food.

Potential Drug Interactions:

AMG 232 (KRT 232) is metabolized by three uridine diphosphoglucuronosyl transferases (UGT1A1, UGT1A3, and UGT1A4) to an acyl glucuronide (M1). In vitro, M1 is not impacted by UGT1A1 polymorphic genotypes UGT1A1*1/*1, UGT1A1*1/*28 or UGT1A1*28/*28.

AMG 232 (KRT 232) is not metabolized by CYP450 isozymes. *In-vitro* study suggests that AMG 232 is a substrate for P-glycoprotein, a competitive moderate inhibitor of CYP2C8, and a time-dependent moderate inhibitor of CYP3A4. M1 is a weak inhibitor of CYP2B6. KRT-232

has the potential to cause a minor drug-drug interaction (DDI) with drugs cleared predominantly by CYP3A4 (inhibition and induction). There is no identified DDI potential for other CYP enzymes. Use caution in patients taking CYP3A4 substrates with narrow therapeutic ranges.

Since AMG 232 (KRT 232) absorption was not impacted in the presence of high pH as demonstrated in a PK simulation, KRT-232 is not likely to be affected by proton pump inhibitor-mediated increase in gastric pH.

In pooled human liver microsomes, AMG 232 (KRT 232) and M1 are moderate inhibitors of UGT1A1. In human hepatocytes, UGT1A1/3/4 enzymatic activities were increased by AMG 232(KRT 232) at concentration $> 5 \mu\text{m}$ and the mRNA transcripts were minimally increased by AMG 232 (KRT 232) at concentration $\geq 10 \mu\text{m}$. Since the exposure of AMG 232 is expected to be low (unbound $C_{\max} = 0.161 \mu\text{m}$ at 480 mg), an increase in metabolism and CL via auto-induction are not expected.

AMG 232 (KRT 232) is not a BCRP substrate. Although AMG 232 (KRT 232) is an inhibitor of OAT3 (moderate to potent), OATP1B1 (moderate to potent), OATP1B3 (moderate to potent), OAT1 (moderate), BCRP (very weak), OCT2 (very weak), and P-glycoprotein (moderate), the ratios of unbound C_{\max} to the in vitro IC_{50} is low (<0.03) at the proposed doses; thus, the potential for AMG 232 (KRT 232) to cause transporter-mediated DDIs due to inhibition of the transporter is low.

Patient Care Implications

Advise women study participants of reproductive potential to use effective contraception while receiving AMG 232 (KRT 232) and 1 month + 1 week (or 5 weeks) after the last dose of AMG 232 (KRT 232). Men study participants must continue to use contraception for 3 months and 1 week (or 13 weeks) after the last dose of AMG 232 (KRT 232). Refer to the protocol document for specific guidance.

Availability

KRT-232 (AMG 232) is an investigational agent supplied to investigators by the Division of Cancer Treatment and Diagnosis (DCTD), NCI.

KRT-232 (AMG 232) is provided to the NCI under a Collaborative Agreement between the Pharmaceutical Collaborator and the DCTD, NCI (see Section 12.3).

Agent Ordering and Agent Accountability

NCI-supplied agents may be requested by the responsible investigator (or their authorized designee) at each participating institution. Pharmaceutical Management Branch (PMB) policy requires that agent be shipped directly to the institution where the subject is to be treated. PMB does not permit the transfer of agents between institutions (unless prior approval from PMB is obtained). The CTEP-assigned protocol number must be used for ordering all CTEP-supplied investigational agents. The responsible investigator at each participating institution must be registered with CTEP, DCTD through an annual submission of FDA Form 1572 (Statement of

Investigator), Biosketch, Agent Shipment Form, and Financial Disclosure Form (FDF). If there are several participating investigators at one institution, CTEP-supplied investigational agents for the study should be ordered under the name of one lead investigator at that institution.

No starter supplies. Sites may order agent supplies when subject enrollment is confirmed. Active CTEP-registered investigators and investigator-designated shipping designees and ordering designees can submit agent requests through the PMB Online Agent Order Processing (OAOP) application. Access to OAOP requires the establishment of a CTEP Identity and Access Management (IAM) account and the maintenance of an “active” account status and a “current” password. For questions about drug orders, transfers, returns, or accountability, call or email PMB any time. Refer to the PMB’s website for specific policies and guidelines related to agent management.

Agent Inventory Records – The investigator, or a responsible party designated by the investigator, must maintain a careful record of the receipt, dispensing and final disposition of all agents received from the PMB using the appropriate NCI Investigational Agent (Drug) Accountability Record (DARF) available on the CTEP forms page. Store and maintain separate NCI Investigational Agent Accountability Records for each agent, strength, formulation and ordering investigator on this protocol.

Useful Links and Contacts

- CTEP Forms, Templates, Documents: <http://ctep.cancer.gov/forms/>
- NCI CTEP Investigator Registration: [contact]
- PMB policies and guidelines: http://ctep.cancer.gov/branches/pmb/agent_management.htm
- PMB Online Agent Order Processing (OAOP) application: <https://ctepcore.nci.nih.gov/OAOP>
- CTEP Identity and Access Management (IAM) account: <https://ctepcore.nci.nih.gov/iam/>
- CTEP IAM account help: [contact]
- IB Coordinator: [contact]
- PMB email: [contact]
- PMB phone and hours of service: [contact] Monday through Friday between 8:30 am and 4:30 pm (ET)

